9.3 Criteria for assessing causality

The site investigator will assess each event for relatedness or causality of the intervention and the event. A guide to grading the degree of certainty about such a relationship is available at www.niaid.nih.gov/ncn/sop/adverseevents.htm. A summary of the grading is as follows:

Unrelated Where the adverse event is clearly not related

Unlikely Where the adverse event does not have a clear relationship to the

intervention

Possible Where the adverse event follows a known pattern of response

Probable Where the adverse event reduces or ceases with withdrawal of the

intervention

Definite Where the adverse event ceased with withdrawal of the intervention and recurs with re-exposure

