5.13 Post study treatments

All participants will be followed by their clinician for continuing care, irrespective of the point at which they exit the study.

Treatment continuation: Melatonin will only be available for currently approved indications (primary insomnia) if the participants meets that indication, after study completion (on discharge). The treatment available to reduce delirium risk after discharge will be determined by the treating clinician, and can include individualised strategies to reduce risk of delirium including regular exercise as tolerated, maintaining vision and hearing or using aids, regular reorientation and non-medication methods to improve sleep (quiet room, relaxation for example).

In all study participants, regardless of above choices, secondary outcomes and collection of data for will occur until the end of the inpatient admission after randomization, unless consent is withdrawn

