9.4 Adverse Event Assessment Diagram

Serious Adverse Events will be reported by the study site, to the local Hospital Research Ethics Committee and to the study coordinating site for study wide reporting. This will occur within 24 hours of first knowledge of the event unless death or life threatening which must be immediate. In addition, events deemed to be both serious and unexpected, and related to the study intervention, will be reported by the coordinating site to the Therapeutic Goods Administration using a 'Blue Form'.

In addition, PaCCSC has a Standard Operating Procedure that describes the reporting of adverse events in detail. The on-line reporting is to be used to enable reporting between sites, local forms of reporting are also to be used for reporting to local sites.

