10.2 Data Safety Monitoring Committee

This study will have a contracted independent Data Safety Monitoring Committee (DSMC). The primary role of the DSMC will be to monitor adverse and serious adverse events. All adverse and serious adverse event reports will be reviewed at 6 monthly intervals, as agreed by the DSMC. In addition, any emerging safety issues will be reviewed by the DSMC on an ad hoc basis if required.

The Data Safety Monitoring Committee (DSMC) will be established to:

- review data from an ethical standpoint, with patient rights, safety and wellbeing being paramount
- consider data from interim analysis where such an analysis is planned
- report on trial continuation

Reports will be provided to the PaCCSC Management Advisory Board and Scientific Committee.

The Data Safety Monitoring Committee (DSMC) will consist of:

- experts in field
- a clinical trials statistician
- a trial pharmacist
- an experienced palliative care physician.

Specifically, the DSMC will receive serious adverse events as part of the established reporting mechanism (email notification of the report from the coordinating site within 24 hours) if the event is unexpected and related to the study intervention. In addition, the DSMC will receive a summary report of all adverse events, these will be discussed as a standing agenda item, with the discussions, actions and outcomes recorded. The DSMC will also receive an updated literature summary at each meeting, which will address new published literature that may have an impact on the study.

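### The causality scale in section 9.3 has no grade for a plausible reaction of a previously unknown type without dechallenge information, so a fatal one can miss regulator reporting

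*Protocol*

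**What the plan says.** Section 9.3 of the protocol asks the site investigator to grade each event on five levels. It points to an external guide on a website and introduces the printed list with "A summary of the grading is as follows". From the top down, the levels work like this:

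- Definite is reserved for an event that stops once the drug is stopped and returns when the drug is given again.
- Probable turns on improvement after the drug is stopped. Its entry opens with "Where the adverse event reduces or ceases with withdrawal of the".
- One step lower, the single condition for Possible is "Where the adverse event follows a known pattern of response".
- Unlikely covers events whose link to the drug is unclear, and Unrelated those with evidently no link.

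Two reporting rules depend on the result. Section 9.4 sets what goes to the Therapeutic Goods Administration: "events deemed to be both serious and unexpected, and related to the study intervention, will be reported by the coordinating site". Section 10.2 has the DSMC notified of a serious event within 24 hours "if the event is unexpected and related to the study intervention".

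The protocol does not say which of the five grades count as related, and it does not define unexpected.

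**The concern.** Expedited reporting to a regulator exists mainly to bring new harms to light. Here the lowest grade that would naturally count as related asks for a known pattern, which pulls against the requirement that the event be unexpected. The two higher grades ask for evidence from stopping or restarting the drug, which a death cannot supply. The scale therefore grades on familiarity and reversibility, not on whether the drug could have caused the event.

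This matters more than usual in this population. Section 9.2.2 notes that participants are expected to die soon and exempts deaths from well-documented decline from serious-event reporting. Separating a drug-related death from a disease-related one depends heavily on the causality judgement, and the printed scale gives the investigator no suitable grade for a new kind of reaction.

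**Working it through.** No sample size, error rate or event count enters this point, so there is nothing to compute. The check is to run typical events through the grades of 9.3 and then through the triggers of 9.4 and 10.2. I take Possible, Probable and Definite as related. That is the natural reading, but the protocol does not state it.

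| Event, serious and plausibly due to drug | Possible (known pattern) | Probable (improves on withdrawal) | Definite (recurs on re-exposure) | Serious, unexpected and related? |
|---|---|---|---|---|
| A. Fatal, type not known for the drug | no | no | no | no |
| B. Fatal, type listed in 9.3.2 (for example seizure), worse than expected | yes | no | no | yes, if unexpected covers severity |
| C. Non-fatal, new type, improves after the drug is stopped | no | yes | no, unless it ceases and recurs on re-exposure | yes |
| D. Lasting disability, new type, partial improvement after the drug is stopped | no | yes, since a reduction is enough | no | yes |
| E. Lasting disability, new type, no improvement | no | no | no | no |

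Rows A and E are the gap. The event is not clearly unrelated, so the only grade left is Unlikely, or none at all. On the literal text it reaches neither the regulator under 9.4 nor the DSMC under 10.2.

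Row B depends on two facts. Section 9.3.2 lists sedation, dizziness, seizure, agitation, anxiety, increased INR and depression as events associated with melatonin, so a fatal event of one of these types has a known pattern. Section 9.2.1 recognises severity beyond expectation as a separate notion, although it does so for disease symptoms. With unexpected undefined, nothing stops such an event from being both Possible and unexpected.

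The routes by which serious events leave the site compare as follows.

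| Route | Section | Depends on causality grade? |
|---|---|---|
| Local ethics committee and coordinating site, within 24 hours, immediately if fatal or life-threatening | 9.4 | no |
| Trial Management Committee, ethics committees and DSMC, within 24 hours | 10.1.1 | no |
| DSMC, e-mail notice within 24 hours | 10.2 | yes |
| DSMC, six-monthly review of all event reports | 10.2 | no |
| Therapeutic Goods Administration | 9.4 | yes |

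The regulator route is the only one with no alternative that is free of the causality filter. For the DSMC, 10.1.1 and 10.2 give different answers on which serious events arrive within 24 hours.

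Probable also has a looseness in the other direction. Under 5.1 and 5.12 the drug ends for every participant at delirium, discharge or three weeks at most, if not sooner. Section 9.3 does not say whether this planned end counts as withdrawal. If it does, a passing event of any cause that fades afterwards fits the wording of Probable.

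**The case against.** The strongest reply is that the five lines are a summary. The investigator is asked for a judgement, the external guide may cover timing and plausibility, and an adverse event SOP is cited in 9.1, 9.4 and 10.1.1. Neither source is available, so the gap may be closed there. This lowers certainty but does not remove the point. The printed lines are the only grading text in the protocol, and they state conditions. Section 9.5.1 asks only whether a post-study event is reasonably related, so the protocol applies a broader test after the study than the one it prints for events during it.

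A second reply is that planned completion is not withdrawal, since 5.12 labels delirium and discharge as completion of study. That reading is open, and one sentence would settle it.

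Four stronger readings are tempting, and the documents do not support them:

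- That no fatal unexpected event could ever be reported to the regulator. Row B shows that a fatal event of a known type can qualify.
- That such a death would go unseen. Sections 9.4 and 10.1.1 circulate serious events without a causality condition, and 10.2 adds six-monthly and ad hoc review.
- That the trial's safety comparison would be distorted. Section 11.3 plans only the incidence of adverse events, with no related and unrelated split.
- That Definite can never be reached. Section 5.13 leaves melatonin available after the study for its approved indication, so re-exposure is conceivable. A top grade that is rarely reached is in any case no defect.

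**Conclusion.** The point holds in limited form. Followed as printed, section 9.3 gives a fatal reaction of a new type no grade above Unlikely. The same applies to a lasting one that shows no improvement. Such an event would not be sent to the regulator under 9.4, nor to the DSMC as an expedited notice under 10.2. One channel, the regulator report, is clearly affected. A second, the DSMC notice, is affected if 10.2 governs over 10.1.1. The documents give no basis for a frequency, and the efficacy result is untouched.

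The conclusion rests on three assumptions: that related means Possible or above, that sites apply the printed lines as conditions, and that neither the unseen guide and SOP nor the diagram named in the heading of 9.4, which is not in the available text, supplies a wider test. The change is worth making because it is cheap and concerns the reporting of new, serious harm.

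**What to change.** In section 9.3, redefine Possible as a reasonable time sequence to study drug where a drug cause cannot be excluded, whether or not the pattern is known. Use dechallenge and rechallenge only as supporting evidence for the higher grades. Add that resolution after the scheduled end of drug is not by itself dechallenge.

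In sections 9.4 and 10.2, state that Possible, Probable and Definite count as related, and define unexpected as unexpected in nature or severity. Reconcile 10.1.1 with 10.2 on which serious events reach the DSMC within 24 hours.

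The cost is protocol and adverse event form wording and a memo to sites. The downside is that somewhat more events will be graded Possible and sent for expedited reporting.

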9.3.1 Time period for assessing AE's and SAE's

At each visit, the participants are encouraged to mention any problems since the last visit. In addition, the following standard questions should be asked;

- 1. Have you had any medical problems since the last visit or study assessment?
- 2. Have you started any new medications, other than given to you in this study, since the last visit or assessment?

For all randomised participants all AE's, irrespective of causality, will be assessed and recorded as per the standard operating procedures. The time period includes the time from randomisation, the inpatient treatment period and the 4 week extension phase (by telephone).

For patients who meet the eligibility criteria and then do not proceed to randomisation, any AE's detected during that window of time, should be reported. If an AE is the reason that a person does not proceed to randomisation, this should be recorded within the CRF, adverse event report and in the clinical record, irrespective of causality or seriousness.

9.3.2 National Cancer Institute, Common Terminology Criteria for Adverse Events.V4.0

These criteria ⁷⁰ have been used to determine adverse events likely to occur during the study period and will be used to determine adverse event reporting and study progress. Criteria specific to the expected events know to be associated with melatonin have been listed below. This is administered by study staff

Symptoms will be identified during each visit using criteria established by the National Cancer Institute, and will be graded accordingly.

Specifically, for this study, the symptoms of interest will be;

[figure not shown]
- Sedation
- Dizziness
- Seizure
- Agitation
- Anxiety
- Increased INR

• Depression

A grade of 3 (that has not responded to symptomatic treatment instituted by the treating physician according to local protocols) or 4 will activate cessation of study intervention and an adverse event report.

All adverse events will be collated by the project officer, and reported to the executive committee on a monthly basis. Adverse event rates will form part of the Key Performance Indicators for the study and will be reported on a regular basis to the Trial Steering Committee and the ethical review boards of the participating sites.

9.4 Adverse Event Assessment Diagram

Serious Adverse Events will be reported by the study site, to the local Hospital Research Ethics Committee and to the study coordinating site for study wide reporting. This will occur within 24 hours of first knowledge of the event unless death or life threatening which must be immediate. In addition, events deemed to be both serious and unexpected, and related to the study intervention, will be reported by the coordinating site to the Therapeutic Goods Administration using a 'Blue Form'.

In addition, PaCCSC has a Standard Operating Procedure that describes the reporting of adverse events in detail. The on-line reporting is to be used to enable reporting between sites, local forms of reporting are also to be used for reporting to local sites.

9.5 Follow-up of AE's and SAE's

After the initial report, investigators are required to follow-up each adverse event and provide further information both to the coordinating centre and the local HREC. All events reported as ongoing are to be reviewed at subsequent visits or appointments in order to report progress and resolution.

All events are to be followed until:

- resolution;
- the condition of the participant stabilises;
- the event can be explained;
- the participant is lost to follow-up;
- death.

Reports are to contain details of follow-up investigations, result reports or reports from other consultations, and are to be updated in a report to the coordinating centre and the local HREC.

9.5.1 Post study AE's and SAE's

A post study event is defined as any event that occurs outside of the time period described in section 9.3 of the protocol. Investigators are required to report any events they become aware of if;

- the event occurs at any time after study participation has ceased, and
- the event is assessed as being reasonably related to the study intervention.

Investigators are not obliged to actively seek events that occur after the study period defined in 9.3.

9.6 Unblinding

In cases of medical need, where urgent medical decisions will be influenced by knowledge of the treatment assignment, the Lead Investigator will have access to the sealed unblinding envelopes and must be contacted in the first place. Clinical staff will be able to discuss the clinical situation with the Lead Investigator to determine the urgency and need for unblinding, and will be informed by the Lead Investigator of the assignment based on these discussions.

In the case of not being able to contact the Lead Study Investigator, the designed staff from PaCCSC should be contacted.

PaCCSC has a Standard Operating Procedure for unblinding (4.7.2, Unblinding), and is to be referred to in the occurrence of unblinding. The PaCCSC coordinating centre will monitor real time unblinding frequency by collecting CRF withdrawal data and unblinding reporting from the Lead Study Investigator.

9.7 Stopping rules

The study will be stopped if new literature indicates findings that can be applied to this question in terms of benefit or side effects, or if reporting of adverse events indicate that review of the study protocol is required, for either or both of the study drugs, or rescue medicine. Two planned interim analyses will be conducted independently and reviewed by the independent data and safety monitoring committee after about 33% and 66% of patients have been enrolled. The primary outcome and adverse events will be compared between groups with p<0.001 required as the threshold of stopping the trial for significant evidence of benefit or harm in either one of the treatment arms.

10.0 TRIAL MONITORING

10.1 Adverse events and efficacy

Adverse events and efficacy for the entire study will be reviewed via a number of mechanisms.

10.1.1 Adverse events

In line with the PaCCSC Standard Operating Procedure for Adverse Events (5.17 Adverse Event Reporting), reports of serious adverse events will be sent to the Trial Management Committee, all participating site Hospital Ethics Review Committees (see Table below) and the Data Safety Monitoring Committee within 24 hours of knowledge of the event, while adverse events will be reported as summary reports as stipulated in the table below.

10.1.1.1 The Trial Management Committee

Each meeting of the Trial Management Committee will receive from the coordinating centre a summary report of the adverse events reported by the investigators. Each summary report will be generated from the on-line entry of adverse event reports by PaCCSC sites. This summary report will be reviewed for reporting compliance, trends in events, and outstanding events that require specific attention. All Trial Management Committee discussions will be minuted, with actions detailed, and reviewed at the subsequent meeting. The chairperson's report to the Scientific Committee will contain a summary of the discussions of the adverse event report and the agreed outcomes. The Trial Management Committee will not have access to unblinded reports of adverse events.

10.1.1.2 Hospital Ethics Review Committees

Adverse events and serious adverse events are to be reported to site HRECs and where appropriate the DSMC in the format and timeframe stipulated by each individual committee.

10.1.2 Efficacy

This study has been adequately powered using available data to ensure a primary efficacy end point that will address the null hypothesis. Interim unblinded analysis is not planned for this study given the impact that this will have on the sample size calculation. An unblinded analysis is likely to increase the need for recruitment and potentially delay the availability of results without addressing the secondary outcomes particularly if the study were to be prematurely closed.

10.2 Data Safety Monitoring Committee

This study will have a contracted independent Data Safety Monitoring Committee (DSMC). The primary role of the DSMC will be to monitor adverse and serious adverse events. All adverse and serious adverse event reports will be reviewed at 6 monthly intervals, as agreed by the DSMC. In addition, any emerging safety issues will be reviewed by the DSMC on an ad hoc basis if required.

The Data Safety Monitoring Committee (DSMC) will be established to:

- review data from an ethical standpoint, with patient rights, safety and wellbeing being paramount
- consider data from interim analysis where such an analysis is planned
- report on trial continuation

Reports will be provided to the PaCCSC Management Advisory Board and Scientific Committee.

The Data Safety Monitoring Committee (DSMC) will consist of:

- experts in field
- a clinical trials statistician
- a trial pharmacist
- an experienced palliative care physician.

Specifically, the DSMC will receive serious adverse events as part of the established reporting mechanism (email notification of the report from the coordinating site within 24 hours) if the event is unexpected and related to the study intervention. In addition, the DSMC will receive a summary report of all adverse events, these will be discussed as a standing agenda item, with the discussions, actions and outcomes recorded. The DSMC will also receive an updated literature summary at each meeting, which will address new published literature that may have an impact on the study.

11.0 STATISTICS

11.1 Null hypotheses to be tested

In people with advanced cancer admitted to hospital there is no difference in delirium-free days with the addition of prolonged release melatonin when compared with placebo

11.2 Statistical analysis of efficacy primary outcome

Intention-to-treat analysis will be used for all statistical comparisons. For the primary outcome, comparisons between groups for delirium-free days, with adjustment to the length of stay and other potential covariates using a general linear model approach will be undertaken. For potential missing data, multiple imputation technique will be applied to handle the missing data. A proper multiple imputation method will be employed that based on various models of assumption including missing completely at random (MCAR), missing at random (MAR), and missing not at random (MNAR). Sensitivity analysis will apply to examine the effects of these different assumptions on the imputed data structure in order to ascertain the most reliable approach.

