11.5 Power and sample size

Sample size was calculated based on the information obtained in the pilot study on the primary outcome, namely delirium-free days during a 3 week study period, and an analytical approach of comparing the mean delirium-free days between groups. It has been estimated that a sample size of 110 in each arm (n=220 in total) would provide 90% power to reject the null hypothesis with a 5% type I error rate to detect an increase of 2 delirium-free days allowing for 30% drop out or loss to follow-up and 5% for possible adjustments for covariates.

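### Section 11.2 uses sensitivity analysis to choose the primary missing-data assumption, a choice that observed data cannot settle between MAR and MNAR

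*Protocol*

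**What the plan says.** Section 11.2 of the protocol holds the only missing-data rule for the primary outcome; the analysis paragraph of the trial summary has none. The primary model compares delirium-free days between arms, "with adjustment to the length of stay and other potential covariates using a general linear model approach will be undertaken". On missing values it says: "For potential missing data, multiple imputation technique will be applied to handle the missing data". The imputation is to rest on "various models of assumption including missing completely at random (MCAR), missing at random (MAR), and missing not at random (MNAR"). The three assumptions stand side by side and none is called primary. The section closes with a sensitivity analysis whose stated purpose is "to examine the effects of these different assumptions on the imputed data structure in order to ascertain the most reliable approach".

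The section gives no criterion for reliability, no MNAR model or size of shift, and no point in time by which the choice must be made. Section 11.5 sets 110 per arm, "allowing for 30% drop out or loss to follow-up and 5% for possible adjustments for covariates".

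**The concern.** A sensitivity analysis normally starts from a fixed primary analysis and asks how far its result depends on an assumption that cannot be tested. Section 11.2 reverses this: the candidate assumptions are run first, and the comparison is meant to show which one to rely on.

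Two things follow. First, the comparison cannot deliver what it promises, because the data hold no information on the choice between MAR and MNAR. Second, with no criterion and no time limit, the text leaves room for the primary result to be selected from several candidates. If that happened with treatment results in view, the nominal 5% error rate on the primary endpoint would no longer be assured.

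**Working it through.** **Inputs from the protocol.** 110 per arm, difference of 2 days, 5% type I error, 90% power, 30% dropout allowance and 5% for covariates (section 11.5). Pilot SDs 3.7 (melatonin) and 6.4 (control) (section 1.3). Root mean square SD = √((3.7² + 6.4²)/2) = 5.23.

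**The plan's own figure.** The missing-data rule has no figure of its own; the nearest is the sample size. Per arm, n = 2(1.960 + 1.282)² × SD²/2². With SD 3.7 this is 72. Then 72/(0.70 × 0.95) = 108.3, rounded up to 109, and 72/0.65 = 110.8, rounded up to 111, so 110 is reproduced. With SD 5.23 the same steps give 144, then 217 to 222. Section 11.5 does not say which SD was used. That is a separate matter; both SDs are carried forward here.

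**Can the comparison identify the assumption?** Suppose missing outcomes follow the observed-data model given arm and covariates, plus a shift d. MAR is d = 0; MNAR is d ≠ 0. The observed outcomes and the pattern of missingness inform the model for observed values and the probability of being missing. The shift d enters neither, so every d fits the observed data equally well. The imputed values differ between the analyses only because d was set differently, so inspecting them returns the assumption that was put in. MCAR differs in one respect: a link between missingness and observed covariates is evidence against it. This does not rescue the rule, since MAR imputation is also valid when MCAR holds.

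**How far can the choice move the estimate?** A shift d applied to a missing share m in one arm moves the treatment difference by about m × d. At 30% missing and 2 days this is 0.30 × 2 = 0.6 days, in either direction, so the candidates span about 1.2 days against a design difference of 2. The same shift in both arms cancels: 0.6 − 0.6 = 0.

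**Type I error if the smallest p-value is taken.** Simulation under no effect, 110 per arm, 1,500 runs per setting, proper normal multiple imputation (20 imputations, Rubin's rules), linear model. Assumptions not in the protocol: one baseline covariate correlated 0.5 with the outcome, missingness dependent on that covariate (so MAR is true), and MNAR shifts of −2 days. The last row is a separate simulation (2,500 runs, 10 imputations, complete-case analysis in place of MCAR imputation). Entries are two-sided rejection rates at 0.05.

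| SD, share missing | MAR fixed in advance | Smallest p of MCAR, MAR | Adding MNAR, same shift in both arms | Adding two MNAR models, shift in one arm only |
|---|---|---|---|---|
| 3.7, about 10% | 4.5% | 5.7% | 6.1% | 13.7% |
| 3.7, about 30% | 5.2% | 6.4% | 7.5% | 42.7% |
| 5.23, about 10% | 4.3% | 5.1% | 5.4% | 8.9% |
| 5.23, about 30% | 4.2% | 5.4% | 6.5% | 23.5% |
| Separate simulation, 30% | 5.6% | – | 8.1% | 26.5% |

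The Monte Carlo standard error near 5% is √(0.05 × 0.95/1500) = 0.6 percentage points. At 30% missing the five estimates differed by 1.2 days on average, as the hand calculation predicts.

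These rates count differences in either direction. The share favouring melatonin (nominal 2.5%) was 2.6% to 3.9% for the best of MCAR, MAR and common-shift MNAR. With the one-arm models added it was 4.0% to 6.9% at 10% missing and 11% to 20% at 30% missing.

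**The case against.** The strongest reply is that section 11.2 refers to the structure of the imputed data, not to the treatment effect or its p-value. Section 5.3 keeps study staff unaware of allocation until the study is complete, so the choice could be made blind. A SAP, not seen here, could fix one assumption. This limits the charge: the text permits a choice driven by results but does not prescribe one. It does not remove the defect. A blind choice between MAR and MNAR would be just as uninformed by the data, and a SAP that fixed one assumption would have to override the stated purpose, not merely fill in detail.

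Three stronger readings are tempting, and the documents do not support them.

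- **The choice is made after unblinding.** The protocol does not say when it is made. The fair criticism is that timing and criterion are open.
- **Control of the type I error is lost, with rates of 24% or more.** Those figures need the smallest of five p-values, two of them from one-arm MNAR models that the protocol does not name. They also need about 30% of primary outcomes to be missing. The 30% in section 11.5 is a sample-size allowance for dropout or loss to follow-up, not a forecast of missing primary outcomes. Section 5.13 continues data collection to the end of the admission after treatment stops, and sections 7.7.2 and 8.9 provide for screening on every shift and daily visits.
- **Imputation would create delirium-free days for people who have died.** Section 11.2 does not say that days after death are missing or will be imputed, and section 7.2 ends the study period at discharge or death. Section 11.5 refers to a three-week period, so how death and discharge count in the endpoint is unclear. That is a separate question of endpoint definition.

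**Conclusion.** The point holds as a fault in a stated rule, not as a missing detail. Section 11.2 asks sensitivity analysis to find the most reliable of three assumptions, two of which observed data cannot tell apart, and so gives it the job of selecting the primary analysis. This conclusion rests on the wording and on non-identifiability; it does not depend on the size of any inflation.

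The inflation is conditional. It is modest if the candidates are MCAR, MAR and an MNAR shift common to both arms, and becomes large only if arm-specific shifts are admitted and much of the outcome is missing. All the rates assume that the smallest p-value is taken, and a normal outcome with one covariate. The real endpoint is bounded by the length of observation and may behave differently.

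**What to change.** Replace the last two sentences of section 11.2 with wording such as:

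*The primary analysis will use multiple imputation assuming that data are missing at random. A complete-case (MCAR) analysis and MNAR analyses (delta-adjusted or tipping-point) are sensitivity analyses. They test the primary result and do not replace it.*

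This drops the clause about finding the most reliable approach. Another primary assumption could be named, provided it is single and fixed in advance. The imputation variables and the range of shifts can be left to the SAP.

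The cost is a wording amendment: no further data and no change in sample size. The trial gives up only the freedom to change the primary missing-data method later.
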